## A. Introduction and Background

It is well documented that children exposed to parental drug use are at greater risk for maladjustment, deviant peer affiliation, and substance use initiation. Parents living with Opioid Use Disorder (OUD) are at high risk for incarceration, family disruptions, health problems, and financial hardship. However, research on drug abuse with men has largely neglected the role of fathering, parenting roles and parenting status for these men. Moreover, our understanding of the unique impacts of opioid misuse on fathering behaviors is even more limited than our knowledge base for mothers. The majority of extant research has been conducted on mothers, although there is evidence that more fathers than mothers enter into drug abuse treatment.

Existing opioid research suggests there are marked parenting differences for fathers and mothers who misuse opioids. Compared to mothers, fathers are more likely to be misusing opioids when they first become a parent, and compared to fathers without a substance use disorder, fathers with OUD exhibit more concerning parenting behaviors and report other limitations that may impact their children. For parenting specifically, compared to fathers without OUD, OUD fathers report lower parental efficacy, engage in fewer positive parenting behaviors such as consistency and positive involvement, and report less satisfaction with the parenting role compared to mothers. Fathers who misuse opioids also report greater prevalence of violence towards their child's mother both over the course of the relationship and report greater violence perpetrated against them by their child's mother.

Within the preventive intervention and treatment research, fathers are vastly underrepresented in studies of parent training relative to mothers, with only a handful of studies including father-related outcomes. Less is known about fathers who do or do not misuse opioids, or what mechanisms are unique to opioid use that interfere with effective parenting. The goal of this pilot is to better understand the unique, specific, influence of opioid misuse on compromised fathering behaviors, and further, how misuse uniquely affects the process of intervention uptake. We will use Fathering Through Change, an evidence-based parenting intervention which has been found to be efficacious for positive changes in fathering mediated by changes in parent efficacy and fathering identity.

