All eligible and consented participants for Procedure 1 will be invited to take three sets of surveys using Qualtrics or RedCap. IP address tracking will be enabled for all surveys in effort to increase security measures and reduce fraudulent survey submissions. First at baseline (pre); second, at 6-weeks later (post); and lastly, at 4 months from baseline (follow-up). Surveys will be conducted online on the participants electronic device and will be formatted for administration on a computer, tablet, or smartphone. Surveys will assess the parent-child relationship, child behavior, parent mental health, parent substance use, intervention knowledge gained and satisfaction, and participant context. The baseline questionnaire will take approximately 95 minutes. The post questionnaire will take approximately 90 minutes. The follow-up questionnaire will take approximate 90 minutes.

These are the steps for participation:

1. Treatment center sends out text messages and emails to current and past male clients. They will not send out text messages and emails to current in-patient clients because these clients do not have access reliable access to technology (not allowed to use it). The text message will contain information to contact the study team. Formal recruitment will occur when the potential participant reaches out to the study team via phone or email. For Facebook and Reddit recruitment, the project coordinator will post the recruitment flyer to groups and communities on both platforms. All interested individuals will contact the project coordinator and complete the formal recruitment process including the eligibility screener.

See **Text Messages** document.

2. For both Procedure 1 and Procedure 2, the study team will respond to interested participants with an enrollment text from a google voice number or study specific email. They will first ask screening questions to determine eligibility. If a participant is eligible, they will provide a link to the electronic survey.

See **Text Messages** document.

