the option to set up a booth might be an effective strategy to be visibly available to anyone walking through. Another example is that outpatient treatment centers might allow us to be present on site before or after groups. For inpatient treatment centers, they might want us to visit during meal times to talk with individuals while they are eating and discuss the research study opportunity. A member of the project team (the PI, RA/Project Coordinator, or Co-I) will use the in-person recruitment script (see "in person recruitment script.docx") provide the participant with an iPad to facilitate the informed consent process and research survey. If we do not have enough iPads at any point, we will encourage individuals to complete the survey on their phone or mobile device. We will have paper copies of the survey as back up if needed or preferred by individuals. All paper copies will be stored in a locked cabinet within a locked room that only the PI has access to. All paper copies will be double-entered for quality assurance. A member of the project team will provide the participant with their incentive upon completion of the survey. Tabling to recruit participants may also happen virtually, if preferred by treatment centers. For virtual tabling, a research assistant will attend online group meetings, with permission from the treatment center, to present the opportunity to participate to clients. Treatment center staff will provide the study flyer to clients and interested individuals will be instructed to contact the study email or phone number. Virtually tabling will occur using secure wifi and using a link provided by the treatment center or the research assistant's HIPAA protected zoom account.

For in person recruitment, all safety protocols will be followed in accordance with the University of Oregon's Stage 1 and 2 Research Activities protocol. The Stage 1 and 2 form will be completed and submitted separately.

Participants who complete procedure 2 (the baseline only survey) will be compensated \$50 via check or gift card in the mail, sent electronically or provided in-person if research is conducted in-person. If participants do not have a mailing address, they will have the opportunity to indicate as such and provide a phone number for the project coordinator to follow-up.

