The funding agency required a Data Safety Monitoring Plan for this research at the time of funding proposal. A copy of the DSMP submitted to the funder is attached; however, it should be noted that there are some discrepancies due to the evolution of the project following proposal. The discrepancies are documented in a separate Memo to File. The key differences are that no information is being obtained from the treatment facilities, and the research no longer plans to include families and children as subjects. We are no longer excluding fathers of children with a developmental disability since children are not research subjects. Only fathers will participate. Additionally, our sample size is now 120 instead of 80. There will be three points of data collection rather than two. All other key components of the DSMP as proposed persist including the defined roles and responsibilities, procedures for monitoring site performance, procedures for monitoring data integrity, protecting confidentiality, and safety reporting and monitoring. Additionally, in the event of a crisis such as expressed elevated suicidality or intent to harm self or other, [name], who is currently receiving supervision to obtain licensure, will create a safety plan with the client (attached) and will make a referral to the appropriate agency such as the emergency department, back to the treatment center they are receiving services from if the client is currently receiving services, a local therapy center such as Options Counseling, or Child Welfare if warranted.

There is no established Data and Safety Monitoring Board/Committee (DSMB/C) as noted in the DSMP.

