**12132019.029**

**A Substance Use Adaptation of Fathering Through Change**

**March 19, 2023**

## Statistical Analysis Plan

Primary outcome hypotheses were tested using standard normal autoregressive, analysis of covariance, models. More specifically, the post-intervention follow-ups were estimated as random intercept models for the 6-week and 4-month follow-ups. For the secondary outcome of substance use count of days or count of use status as a binary outcome, generalized linear models were estimated. Given the small sample size and two waves of repeated measures for the random intercept, models were estimated using robust standard errors to address nonindependence. Evaluation of the 5 primary outcomes were corrected for false discovery rate (Benjamini & Hochberg, 1995). Missing data patterns were evaluated to assess random missingness. with Little's MCAR test (Little, 1988). Little's MCAR test revealed that the data were missing completely at random and the estimated means and covariances for partial data fathers was not significantly different than fathers' with complete data ( $\chi^2(168) = 193.99$   $p = .083$ ).

Benjamini, Y., & Hochberg, Y. (1995). Controlling the False Discovery Rate: A Practical and Powerful Approach to Multiple Testing. *Journal of the Royal Statistical Society. Series B, Methodological*, 57(1), 289-300. doi:10.1111/j.2517-6161.1995.tb02031.x

Little, R. J. A. (1988). A test of missing completely at random for multivariate data with missing values. *Journal of the American Statistical Association*, 83(404), 1198-1202.

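### Substance use at follow-up can go missing because the father returned to use, and the SAP has no sensitivity analysis for this

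*SAP*

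**What the plan says.** **Outcome and model.** The SAP (Statistical Analysis Plan) names substance use as the secondary outcome: "For the secondary outcome of substance use count of days or count of use status as a binary outcome, generalized linear models were estimated". It adds robust standard errors for the repeated measures. On missing data it reports only Little's test, chi-square 193.99 on 168 df, p = .083, and concludes that the data were MCAR.

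**Collection.** Protocol section C sets three Procedure 1 surveys: "First at baseline (pre); second, at 6-weeks later (post); and lastly, at 4 months from baseline (follow-up". The mode is stated once: "Surveys will be conducted online on the participants electronic device and will be formatted for administration on a computer, tablet, or smartphone".

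**Inpatient access.** Step 1 of the same section explains why treatment centers do not message current inpatients: "these clients do not have access reliable access to technology (not allowed to use it".

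**Other routes.** Section D, under Procedure 2, describes iPads, site visits (inpatient centers included) and paper: "We will have paper copies of the survey as back up if needed or preferred by individuals". Nothing similar is described for the Procedure 1 follow-ups. Section G says treatment facilities supply no data to the study.

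**Population.** Fathers enter Procedure 1 after anything from 1 day to just under 18 months of abstinence (section D). Section A says: "Parents living with Opioid Use Disorder (OUD) are at high risk for incarceration, family disruptions, health problems, and financial hardship".

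**The concern.** The event that the outcome measures can also stop it from being recorded. Some fathers enter very early in abstinence, so a return to use during follow-up is foreseeable, and inpatient care is one possible consequence. The protocol itself describes inpatient care as a setting where the survey technology is not allowed. Custody may have the same effect, but that is inferred from the stated risk of incarceration; no section describes device access in custody.

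If such fathers are lost, an analysis of the reported values understates use. If users are lost at the same rate in both arms, a real difference tends to shrink. If the rates differ, a difference can appear, shrink or grow, in either direction. Robust standard errors address the correlation between waves, not this selection. The reader of the results also has the SAP's statement that the data were MCAR, which is reassuring on exactly this point.

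**Working it through.** **1. The SAP's own figure.** The upper tail of chi-square on 168 df at 193.99 is 0.0828, which rounds to .083, so the p-value reproduces. The 5% critical value is 199.24, so MCAR is not rejected at 5%. That is not evidence that MCAR holds. The test compares means and covariances of observed values across missingness patterns, so it cannot detect loss that depends on a use value nobody reported.

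**2. Inputs.** Section D (Procedure 2) gives 41 fathers enrolled in Procedure 1, about 20 per arm if balanced. The documents give no use rate, readmission rate or missing-survey count. All rates below are assumptions.

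**3. Users lost from one arm only.** Assume 20 fathers per arm, 8 users in each (40%, no true effect), and k users in one arm unreachable. Observed use in that arm is (8 − k)/(20 − k), against 8/20 = 40.0% in the other.

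| k | Observed use | False difference (points) |
|---|---|---|
| 1 | 7/19 = 36.8% | 3.2 |
| 2 | 6/18 = 33.3% | 6.7 |
| 3 | 5/17 = 29.4% | 10.6 |
| 4 | 4/16 = 25.0% | 15.0 |

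For scale, the standard error of a difference at 40% with 20 per arm is √(2 × 0.4 × 0.6/20) = 0.155, or 15.5 points. The bias at k = 4 is about one standard error.

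**4. Users lost from both arms.** Let p be true use, mU the share of users missing and m0 the share of non-users missing. Observed use = p(1 − mU)/[p(1 − mU) + (1 − p)(1 − m0)]. Take p = 40% control and 20% intervention (a true 20-point difference), with m0 = 10%.

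| mU, both arms | Observed control | Observed intervention | Difference (points) |
|---|---|---|---|
| 10% | 40.0% | 20.0% | 20.0 |
| 30% | 34.1% | 16.3% | 17.9 |
| 50% | 27.0% | 12.2% | 14.8 |
| 70% | 18.2% | 7.7% | 10.5 |

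With p = 40% in both arms and mU = 50% in one and 30% in the other, observed use is 0.20/(0.20 + 0.54) = 27.0% and 0.28/(0.28 + 0.54) = 34.1%, a false difference of 7.1 points. Its sign depends on which arm loses more users.

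**5. What scoring missing as use does.** The scored rate is p + (1 − p)m0, which does not depend on mU. In the 40% versus 20% case it is 0.40 + 0.60 × 0.10 = 46% against 0.20 + 0.80 × 0.10 = 28%, an 18-point difference in every row of the table. With 40% in both arms and equal m0 the difference is 0.

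It has its own weakness. If non-users go missing at 10% in one arm and 20% in the other, it gives 46% against 0.40 + 0.60 × 0.20 = 52%, a false 6 points. This is why the assumed use among missing fathers should also be varied by arm.

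**The case against.** **Points that stand.** The technology remark explains a recruitment rule; it was not written about follow-up. No survey window is stated, so a short stay need not cost a survey. The contact schedule and the measures list are separate documents not available here, so the recall period behind the count of days is unknown, and a later survey might cover part of an absence. If the substance use model pools both waves, which the SAP leaves unclear, a father who misses one wave still contributes the other. The outcome is secondary, in a pilot. For these reasons the claim is that such fathers may be unable to respond, not that they cannot.

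**Stronger readings that the documents do not support.**

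- *The bias favours the intervention.* A reader might infer this because the clinician has planned contact only with intervention fathers and may refer a father "back to the treatment center they are receiving services from if the client is currently receiving services". In section G the trigger is a crisis such as suicidal thoughts or threatened harm, not a return to use. The treatment center is one of several destinations, and nothing says that the referral leads to inpatient care.
- *A few fathers would reverse a significant result.* One can invent counts such as 8/20 against 2/18, where Pearson's test gives p = 0.043. Fisher's exact test gives 0.067 and the continuity-corrected test 0.099, so the example depends on the test chosen, and neither test is the SAP's model.
- *The 168 df show how many fathers had incomplete data.* Any such count depends on the number of variables in the test, which the SAP does not give.

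**What remains.** None of this supplies a second data source, a rule for unreturned surveys or a sensitivity analysis.

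**Conclusion.** The concern holds in a limited form. The protocol describes a setting that a father may enter after returning to use and in which the survey technology is not allowed. It describes no other way of measuring Procedure 1 substance use, and the SAP answers missing data only with a test that cannot detect loss of this kind. Missingness can therefore depend on the unreported outcome.

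The size and direction of any bias are unknown, because the documents give no missing-survey counts, reasons or use rates. The shifts of about 3 to 15 points assume 20 fathers per arm, 40% use in both and losses in one arm only; they show sensitivity at this sample size and do not estimate what happened. The inpatient barrier is documented, while the custody barrier is inferred.

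The same absences would affect the five primary outcomes, but the link between event and missing value is most direct for substance use. The point should be addressed before a substance use result is interpreted, with medium confidence in its practical weight.

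**What to change.** 1. Beside the existing model, add an analysis of yes/no substance use with every missing follow-up scored as use, by the same rule in both arms. Label it post hoc, since the SAP is dated March 2023 and already reports a result.
2. Ideally, also vary the assumed use rate among missing fathers separately by arm, and show where the conclusion changes.
3. Call the substance use result robust only if the analyses agree.
4. Report missing surveys by arm and wave, with reasons (inpatient care or custody among them) where known.
5. Reword the MCAR statement to say that MCAR was not rejected.

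The cost is one SAP paragraph, one extra model on data already held and one small table; step 2 adds a few further runs. The downside is that scoring missing as use overstates use for fathers missing for other reasons and can mislead if those losses differ by arm. It belongs beside the available-data model as a sensitivity analysis, not in its place.

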## C. Methods, Materials and Analysis

This study will include two procedures; Procedure 1 is for the intervention study and Procedure 2 is for the baseline study.

Procedure 1 for the intervention study is a randomized-control trial of the Fathering Through Change (FTC) intervention. Our goal is to recruit up to 120 participants and randomly assign them to either intervention or control. Treatment centers throughout the state of Oregon will help to facilitate recruitment. They will do outreach to men currently receiving treatment services and to men who have received treatment from the respective treatment centers in the past. Individuals who receive communication from a treatment center may also share that information with their peers in recovery. Those individuals will also be welcome to participate if they meet the inclusion/exclusion criteria. The clinician does not have to be vetted by in order to provide services for men currently receiving treatment since they are not an employee of any treatment center and have been vetted by the University of Oregon. Additionally, the study will recruit participants by advertising on social media websites, specifically Facebook and Reddit. Public account pages will be made on each platform to advertise the current study. The recruitment flyer and posted text (see "Fathering Through Change (FTC) Intervention Research Study.pdf" and "Facebook or reddit example posting.docx" will be posted on both platforms. For Facebook, the flyer and posted text will be posted to groups related to heroin/opioid/substance use recovery and parenting. For Reddit, a similar process will occur, such that the flyer and posted text will be posted to "communities" that relate to heroin/opioid/substance use recovery and parenting in recovery. In addition to the flyer and posted text, contact information will be shared that can connect interested individuals with affiliated research personnel. All individuals expressing interest in the study will be directed to contact the project coordinator to complete the eligibility screener.

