3. The first page of the survey will take participants to a screener to ensure they are eligible to participate. We will screen for past 18 month (Procedure 1) and 36 month (Procedure 2) abstinence from illicit substance use (For Procedure 1, must have less than an 18 months of abstinence from illicit substances. For Procedure 2, must have less than a 36 months of abstinence from illicit substances), child in appropriate age range and at least two hours per week spent with child. Regarding Procedures 1 and 2, participants who are ineligible will be taken to the end of the survey and will not receive follow-up. Participants who are eligible will complete the informed consent process electronically. After consenting, they will take the baseline questionnaire survey. In the baseline survey, we will include a questionnaire related to the psychological and parenting consequences of COVID-19 (see "Measures Overview\_8\_31\_20.docx") to better understand the impacts of COVID-19 on fathers' parenting, ability to care for their child(ren), distress, and potential substance use cravings and use.

4. For both Procedures 1 and 2, during the survey, they will provide their contact information so that they can receive either an electronic gift card or check in the mail, depending on their preference as an incentive. This information will also be used to provide them with study materials, reach out for follow-up surveys (Procedure 1), and link participant data overtime (Procedure 1).

5. For Procedure 1, once they have completed the questionnaire, they will receive a follow-up text message and email (at least one method depending on information given) within one week to welcome them to the study. Different messages will be provided depending on whether a participant is assigned to the control or intervention group. Random assignment will occur using a random number generator in batches of 10 (up to 100 pre-determined for eligible participants- assigned at the time of enrollment) to ensure the design is balanced if our sample size is smaller than expected.

6. For Procedure 1, the PI will provide videos to the participant on a weekly basis for 6 weeks. The participant will have the opportunity to take a brief knowledge test after watching each video to earn an additional \$5 per knowledge test completed. The PI will schedule appointment for the coach to call via text or email with participants.

See **Text Messages** document.

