#### **D. Research Population & Recruitment Methods**

**Procedure 1 (Intervention Study):** The participant population are fathers who are in recovery from substance use disorders and have been abstinent from illicit substances for less than 18 months. Participants must be over the age of 18 years old. Our primary intervention target is fathers with opioid use disorder and efforts will be made to prioritize fathers who have specifically misused opioids in the past.

Fathers are eligible to participate if:

1. They identify as being in recovery and have been abstinent from illicit substances for at least 1 day and less than 18 months.
2. They have parenting responsibilities for a child between the ages of 3-16 who they spend at least 2 hours per week with.
3. They speak English.
4. They are 18 and older.

The project coordinator will complete the eligibility screener via text message or phone call. Individuals will be asked to describe their recovery and family situation to the project coordinator through open ended questions. Individuals will be excluded if they do not meet eligibility criteria, or if they deny answering questions about their recovery and family situation. Individuals will be excluded if they cannot speak English because they will not be able to understand intervention content and will not be able to participate in surveys. Father's must have potential to have some contact following treatment since the intervention is targeted at improving parenting skills. Fathers of children younger than 3 or older than 16 will be excluded because the intervention is not suitable for children outside of the age range 3-16.

The total number of participants will not exceed 80 for procedure 1. Our goal is to recruit approximately 40 fathers to the intervention condition and 40 fathers to the control condition. This will provide enough data to compare effectiveness between condition and also to examine the effects of different substances on intervention outcomes. We expect these numbers may be less due to COVID-19.

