The total number of participants will not exceed 120 for the baseline only survey. This number includes the participants who also participated in procedure 1 so we would recruit 120-number recruited for procedure 1. We anticipate that recruitment is finished for procedure 1 and we have enrolled only 41 subjects, thus, we expect that no more than 79 participants will be recruited for the baseline only survey.

Similar procedures for virtual recruitment from procedure 1 will be followed in the event of virtual recruitment for procedure 2. For procedure 2, the project team may travel to treatment centers to complete the eligibility screener and offer the chance to complete the survey in person via an iPad. Treatment centers will allow the research team to be present on site, and will provide an indoor or outdoor space that allow for sufficient spacing and privacy to mitigate risks associated with COVID-19 transmission and loss of privacy. The treatment centers will let fathers know that the study team is on site and fathers will voluntarily approach the study team in a location where the study team is not able to see treatment center attendees to mitigate HIPAA privacy concerns. We will work with treatment centers who consent to in-person recruitment to determine the best process to talk with clients while on site. This might vary based on the type of treatment center. For example, the Methadone clinic has people coming and going regularly, thus

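### The five primary tests rest on robust standard errors in a small sample, with no small-sample correction or t reference named; if none was used, they are mildly too liberal at about 41 fathers

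*SAP*

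**What the plan says.** The SAP (Statistical Analysis Plan) describes the primary models as baseline-adjusted random-intercept models over the 6-week and 4-month follow-ups. On standard errors it says: "Given the small sample size and two waves of repeated measures for the random intercept, models were estimated using robust standard errors to address nonindependence". On multiplicity it says: "Evaluation of the 5 primary outcomes were corrected for false discovery rate". It refers to "the estimated means and covariances for partial data fathers", so some fathers have incomplete data, but it gives no missing rate. It does not state the type of robust error, a finite-sample correction, a reference distribution, degrees of freedom, the FDR level, the covariates beyond baseline, or the number of fathers analysed.

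The protocol does not fill the gap. The Analysis Plan paragraph in section C lists t-tests, ANCOVAs, MANOVAs and path models only. On sample size, section D under Procedure 2 reports that "we have enrolled only 41 subjects" in Procedure 1. Section D under Procedure 1 says "The total number of participants will not exceed 80 for procedure 1", while section C says "Our goal is to recruit up to 120 participants and randomly assign them to either intervention or control". The 41 is the only enrolment count; 80 and 120 are planned maxima.

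**The concern.** The cluster here is the father, so the number of clusters is at most the number of fathers analysed. The usual cluster-robust (sandwich) variance is built from fitted residuals, which are smaller on average than the true errors. The variance is therefore biased downward, by an amount that grows as clusters become fewer. A normal reference adds to this by ignoring the uncertainty in the estimated variance. The SAP gives the small sample as part of its reason for robust errors, and a small sample is where the uncorrected form does worst.

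Benjamini-Hochberg does not repair this. It takes the five p-values as valid; if they are slightly too small, so are the adjusted ones. At stake is a borderline adjusted p-value on one primary outcome when few or no outcomes respond.

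**Working it through.** The documents state no error rate or power figure on this point, so there is nothing to reproduce. The check asks what the tests would do under each version of the robust error.

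**Inputs from the documents.** Five primary outcomes, Benjamini-Hochberg, two follow-up waves, a baseline-adjusted random-intercept model (SAP); 41 fathers, with 80 and 120 as the range (protocol sections C and D). Equal arms are taken from "Random assignment will occur using a random number generator in batches of 10" and the stated aim of balance.

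**Assumed, not in the documents.** Two-sided 5% tests; FDR level 5%; 0, 25 or 40% missing per wave, completely at random; correlation 0.6 between baseline and follow-up, 0.6 between follow-ups, 0.4 between outcomes; fixed effects for condition, baseline and wave only.

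**Step 1, by formula.** With three between-father parameters (intercept, condition, baseline), the uncorrected variance is too small by roughly (N-3)/N. The true size of a nominal 5% test against z is then about

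2 × P(t with N-3 df > 1.96 × √((N-3)/N)).

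For N = 41: 1.96 × √(38/41) = 1.96 × 0.963 = 1.887, which gives 6.7%. The same formula gives 5.8% at N = 80 and 5.5% at N = 120. The strictest Benjamini-Hochberg step for five tests is 5%/5 = 1%. There the cut-off is 2.576 × 0.963 = 2.480, and the true size at N = 41 is 1.8%. The relative excess is thus largest where a single-outcome claim is decided.

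**Step 2, by simulation.** Null case, 41 fathers, 20,000 runs per main scenario, Monte Carlo error about 0.2 points on any rejection. CR0 is the uncorrected sandwich variance. CR1 multiplies it by G/(G-1) × (N-1)/(N-4), where G is fathers with data and N is now observations. CR2 adjusts the residuals for leverage. The t reference has G-3 df, except for CR2, which uses Satterthwaite df. Entries are for 0 / 25 / 40% missing per wave.

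| Method | Rejection per nominal 5% test, % | Any Benjamini-Hochberg rejection, % |
|---|---|---|
| CR0, z | 6.7 / 7.1 / 7.7 | 8.3 / 9.2 / 10.1 |
| CR0 × G/(G-1), z | 6.5 / 6.8 / 7.3 | 7.7 / 8.6 / 9.5 |
| CR0, t | 6.0 / 6.2 / 6.6 | 6.1 / 6.9 / 7.4 |
| CR1, t | 5.3 / 5.4 / 5.5 | 5.2 / 5.4 / 5.9 |
| CR2, Satterthwaite t | 5.0 / 5.1 / 5.2 | 4.7 / 5.0 / 5.1 |

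**Step 3, larger samples.** With 25% missing, CR0 with z gives 6.1% per test and 6.7% for any rejection at 80 fathers, and 5.6% and 5.8% at 120.

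**Step 4, when some outcomes respond.** With 2 of 5 outcomes at a true 0.5 SD, 41 fathers and 25% missing, the FDR is 5.1-5.3% for CR0 with z, 3.1-3.3% for CR1 with t and 2.9-3.1% for CR2.

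**Step 5, sensitivity.** At 41 fathers and 25% missing, any rejection with CR0 and z is 9.6% with uncorrelated outcomes, 7.7% with outcome correlation 0.7, and 9.4% with correlations of 0.4 (baseline) and 0.5 (follow-ups). At an FDR level of 10%, any rejection is 14.1-16.5% (CR0, z), 9.9-10.5% (CR1, t) and 9.3-9.8% (CR2). A separate simulation with different code gave 6.6-7.3% per test for CR0 with z at 41 fathers, across 0-30% missing, unequal variances and skewed errors, and 8.1% with four baseline covariates. Extending the Step 1 formula to five null tests with outcome correlation 0 to 0.5 gave 7.6-8.8% for any rejection, against 4.6-5.0% with a correction and t.

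**The case against.** The strongest reply is that this is silence, not a shown error. The SAP is a one-page summary in the past tense, and many such summaries omit the finite-sample variant. The ANCOVA and t-test language in the two documents is at least as compatible with a t reference as with z. With t alone, any rejection falls to 6.1-7.4%; with CR1 and t, to 5.2-5.9%. That stands: every inflation figure is conditional on uncorrected errors with z.

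Three further limits also stand. The 10% figure needs 40% missing per wave, a rate that no document gives. The analysed number is not established as 41: the protocol only anticipates that recruitment to Procedure 1 is over, section C leaves open re-contacting Procedure 2 fathers for the trial, and attrition could lower it. And a fixed df of fathers minus 3 presumes a covariate set that the SAP does not list.

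The study is also a pilot asking whether the intervention shows promise, and about two percentage points per test is unlikely to overturn that judgement. This limits the weight of the point but does not answer it. A reader still cannot tell whether a borderline adjusted p-value is sound, and a better-behaved method exists for the same five models.

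**Conclusion.** The point holds in conditional form and is minor to moderate. The SAP relies on robust errors in a sample it calls small and names no correction or t reference. If the errors were uncorrected with a normal reference, then at about 41 fathers the per-test error is about 6.7-7.1%, and the chance of any primary claim under a complete null is about 8-9% (5% FDR level, 0-25% missing). The assumed correlations and covariates shift these figures but not the direction.

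A reader might infer more, and the documents do not support it:

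- That the reported p-values are wrong. Nothing says which variant or reference was used.
- That FDR control has failed. With 2 of 5 outcomes truly affected, the FDR stays within about 0.3 points of the assumed 5%.
- That robust errors were the wrong choice. They are a reasonable response to repeated measures; only the small-sample form is in question.

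**What to change.** For the five primary models, compute p-values and confidence intervals with CR2 cluster-robust errors and Satterthwaite df. CR1 with t on fathers minus the number of between-father parameters actually fitted performs almost as well when arms are equal. Under a 15-of-41 split, which no document reports, any rejection was 6.1% with CR1 and t and 4.8% with CR2, so CR2 is the safer default. Apply Benjamini-Hochberg to those p-values, and state the FDR level, the df and the number of fathers analysed. If such a correction was already used, name it; no re-analysis is then needed.

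The cost is one SAP sentence and, if no correction was used, one re-run of five existing models. At 41 fathers, intervals are 7-9% wider with CR1 and t and 8-11% wider with CR2 than uncorrected z intervals. The formula for complete data agrees at the lower end: (2.024/1.960) × √(41/38) = 1.033 × 1.039 = 1.073. At 80 fathers the widening is 4% with either.

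Nominal power also falls. In the 2-of-5 scenario at 41 fathers, power per true effect is 36% (CR1, t) or 34-35% (CR2), against 44% uncorrected; at 80 fathers it is 72% and 71% against 75%. The loss at 41 is the price of removing excess error: with uncorrected z held to a 5% any-rejection rate under the null (Benjamini-Hochberg level 2.1%), power is 33%.
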